Type I error. The significance level will be 0.025 for the 1-tailed noninferiority tests for the primary outcome and for each set of the secondary outcomes, and 0.05 for each of the 2-tailed superiority tests for tertiary outcomes (i.e., no adjustment for multiple testing for tertiary outcomes).

Our primary hypothesis is that HES 130/0.4 is noninferior to standard care effects on **mean urinary NGAL** measured within one hour of arrival to ICU and 24 following completion of surgery. We a priori define the noninferiority delta for urinary NGAL as a ratio of geometric means (since NGAL data are expected to be lognormal) of 1.15, for an effective delta of 15% of the control group mean. [Note: for this and other outcomes, if the data are non-normal, a log-transformation will be attempted and the treatment effect (if normal on the log-scale) will be summarized as the ratio of geometric means, equivalent to the difference in means of the log-transformed data.] As noted below under “Continuous outcomes measured over time (Primary and Secondary Aims)”, we will assess the treatment effect for the primary outcome in the context of a linear mixed model which allows us to simultaneously assess the effect across the collapsed time points if there is no group-time interaction, or else at specific times if there is an interaction detected. We will conduct tests for noninferiority using treatment effect estimates from the linear mixed model and applying 1-tailed t-tests for noninferiority as described in Mascha and Sessler (2011) [Mascha EJ, Sessler DI: Statistical grand rounds: Equivalence and noninferiority testing for regression models and repeated measures designs. Anesth Analg 2011; 112: 678–87], and with t-statistic as follows:

$$T_{NI} = \frac{\hat{\beta}_1 + \delta}{SE_{\hat{\beta}_1}}, \text{ where } \hat{\beta}_1 \text{ is the estimated treatment effect with standard error}$$

$SE_{\hat{\beta}_1}$ and noninferiority delta of δ .

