Time to event outcomes. Randomized groups will be compared on time to event outcomes including duration of mechanical ventilation, duration of stay in the intensive care unit, and duration of hospital stay using Cox proportional hazards regression models adjusting for any baseline imbalances covariables. For these models the outcome will be time to experiencing the event while alive, i.e., time to removing the ventilator, discharge from the ICU and discharge from the hospital. Patients who die before the event occurs will be listed as failures (i.e., no event) and censored at a time just beyond the last observed event for any patient. Ignoring the deaths or censoring at the time of death may introduce bias.

Binary outcomes. Groups will be compared on binary outcomes, including in-hospital cardiac, renal, infection, or neurologic morbidity, and overall major morbidity (including death), using either logistic regression (to adjust for baseline imbalance as needed) or Pearson chi-square or Fisher's exact test, as appropriate. However, the study is not powered for assessing binary outcomes, and these analyses particularly will be interpreted with caution (whether significant or not).

For all analyses, confidence intervals for the estimated treatment effect will be provided, and these, along with the point estimates of treatment effect, will be emphasized in our reporting. SAS statistical software (Carey, NC) and R software version 2.8.1 for Windows (The R Foundation for Statistical Computing, Vienna, Austria) will be used for all statistical analyses.

Missing data. If primary or secondary outcome data are missing we will use multiple imputation of outcome values based on all available data before the time point of interest. As a secondary analysis we will conservatively assign the worst observed value for the given time point across all patients to an HES patient and best observed value to a control patient. If there is a non-trivial amount of missing outcome data we will also conduct sensitivity analyses on various forms of imputation (from none at all to full multiple imputation). However, we will work hard to avoid missing outcome data. If baseline data not included in the analyses are missing we will simply describe the missingness.

Sensitivity analyses. We will conduct a sensitivity analysis for the primary outcome that adjusts for time on CPB, length of surgery and intraoperative hypothermia.

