Interim monitoring analyses. We will conduct interim analyses for the parameter urinary NGAL (assessing safety [i.e., noninferiority] and non-safety [i.e., noninferiority not found]) at every 1/6th (16.7%) of the maximum enrollment of 130 patients, or approximately at every 22 or 23 patients, in a group sequential design. We will use the gamma spending function with gamma of -5 for safety (alpha spending; very conservative, like O-Brien-Fleming boundaries) and gamma of 0 for futility, or non-safety (beta spending; fairly aggressive, like Pocock boundaries). We spend the beta faster than the alpha in order to be able to detect any potential harm of the treatment as early as possible in the trial. Table 3 gives the P-value boundaries for efficacy and futility at each interim look (columns 5 and 6). Column 2 gives the total sample size at each look. The last 2 columns give the probability of crossing a boundary when the null hypothesis is true (Under H0) and when the alternative (noninferiority) is true (H1). For example, if Voluven is truly noninferior, the probability of crossing the safety boundary is 3.1% at the first look, $3.1\% + 12.7\% = 16\%$ through the second look, and so on. The below figure displays the boundaries on the z-scale (A) and the error spending functions (B) for this design.

Table 3. Interim Monitoring -- Group Sequential Design Boundaries							
Information action	Cumulative Accrual	Alpha Spent	Beta Spent	P-value Boundaries		Boundary Crossing Probabilities	
				Safety H0	Non-safety H1	Under H0 For nonsafety	Under H1 For safety
0.167	22	0.0004	0.017	<0.001	0.746	0.254	0.031
0.333	43	0.001	0.033	0.001	0.471	0.303	0.127
0.500	65	0.003	0.050	0.002	0.256	0.217	0.229
0.667	86	0.006	0.067	0.005	0.125	0.122	0.252
0.833	108	0.013	0.083	0.010	0.056	0.060	0.183
1.000	130	0.025	0.100	0.021	0.021	0.025	0.078

A. Z-statistic Stopping boundaries

B. Alpha and beta spending functions

Sample size calculations (Aim 1):

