Sample size is based on assessing the noninferiority of HES 130/0.4 to 5% albumin on the primary outcome of urinary NGAL. In patients undergoing cardiac surgery, Koyner et al (2012)²⁹ observed median [quartile] urinary NGAL values of 28.3 (13.5–82.9) in patients who did not progress to renal failure and 72.1 (11.4–495.6) in patients who progressed to renal failure. Assuming that NGAL values follow a log-normal distribution as in previous studies, we can use the above observed quartiles to estimate the mean, standard deviation and coefficient of variation (CV) for the above groups, yielding CV of 2.3% and 50%, respectively. Assuming for the current study a coefficient of variation between these values, or 25%, we would need 52 patients per group (total of 104) to have 90% power at the 0.025 significance level to be able to claim noninferiority of HES to albumin using a noninferiority delta of a ratio of geometric means of 1.15. These calculations assume no treatment-time interaction and therefore no Bonferroni correction for comparing groups at each of two time points within an outcome. Based on the above calculations, a sample size of 110 would suffice for a study with no interim monitoring. **Adjusting for the interim monitoring at each one-sixth of the total, a maximum sample size of 130 patients are required. Allowing for 5 potential dropouts and 5 pilot patients (which will not be included in the analyses), we will plan for a potential total of 140 patients.**

STUDY PROCEDURES

Quality Assurance

The major components of quality assurance will be staff training, the standardization of data collection, entry, and processing, and ongoing monitoring to ensure timeliness and accuracy of study data. All study protocols and forms will be compiled into two operations manuals (one for the clinical sites and one for data management) that will be revised as necessary. A clinical reference manual will be created and will include administration and scoring criteria, specific testing instructions and inclusion and exclusion criteria for diagnosis and study ascertainment. This manual will also contain copies of test forms and will be available to all study personnel from a password-protected web site. The current manual for data management will be made easily available to data management personnel and used for continued training. This manual will include a question-by-question written script for interviewing purposes.

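### No stopping-adjusted estimate or interval is specified for urinary NGAL: after the six-look design an ordinary 95% interval covers a true ratio of 1.00 in about 89% of trials, although the noninferiority error rate is not inflated

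*Combined protocol and SAP*

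**What the plan says.** All references are to STATISTICAL METHODS in the combined protocol and SAP, unless stated.

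- **Reporting (paragraph after Binary outcomes).** Across all analyses, "confidence intervals for the estimated treatment effect will be provided, and these, along with the point estimates of treatment effect, will be emphasized". No confidence level and no interval method are given.
- **Type I error.** "The significance level will be 0.025 for the 1-tailed noninferiority tests for the primary outcome". The margin is set there too: "We a priori define the noninferiority delta for urinary NGAL as a ratio of geometric means" of 1.15. The effect and its standard error come from the linear mixed model, described further under Continuous outcomes measured over time.
- **Interim monitoring analyses.** NGAL is examined "at every 1/6th (16.7%) of the maximum enrollment of 130 patients". On the spending functions: "We will use the gamma spending function with gamma of -5 for safety", and "gamma of 0 for futility, or non-safety (beta spending; fairly aggressive, like Pocock boundaries". Table 3 converts these into P-value boundaries and crossing probabilities.
- **Sample size calculations (Aim 1).** Because of the interim looks, "a maximum sample size of 130 patients are required".

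The plan names no repeated, stage-wise or bias-adjusted interval or estimate. Its Bonferroni corrections concern the post-baseline measurement times and the Secondary Aim 1 endpoints, not the interim looks.

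**The concern.** A trial that stops when its statistic crosses a boundary tends to stop on a favourable or unfavourable fluctuation. The ordinary estimate at that moment is pulled towards the boundary that was crossed, and the usual estimate ± 1.96 SE no longer has its nominal coverage. Group-sequential boundaries protect the test; they do not repair the estimate or the interval.

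Here the plan chooses to lead with the estimate and interval, and early stopping is the expected course. At a true ratio of 1.00, the case the design is powered on, about 91% of trials stop before the sixth look. What is at stake is how the size of the kidney effect is read: an equivalent fluid can be reported with an interval that suggests renal harm or, less often overall, renal benefit.

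**Working it through.** **1. Reproduce Table 3.** Inputs: six equal looks, one-sided alpha 0.025, beta 0.10, margin log 1.15 = 0.1398, gamma-family spending. Let Z = (log 1.15 − log estimated ratio)/SE, so that large Z favours noninferiority. Recursive integration with alpha-spending gamma −4, beta-spending gamma 0 and a non-binding non-safety boundary gives:

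| Look | Safety Z (P) | Non-safety Z (P) | Safety crossing at ratio 1.00 |
|---|---|---|---|
| 1 | 3.325 (0.0004) | −0.663 (0.746) | 0.031 |
| 2 | 3.103 (0.0010) | 0.073 (0.471) | 0.127 |
| 3 | 2.860 (0.0021) | 0.656 (0.256) | 0.229 |
| 4 | 2.603 (0.0046) | 1.152 (0.125) | 0.252 |
| 5 | 2.330 (0.0099) | 1.592 (0.056) | 0.183 |
| 6 | 2.035 (0.0209) | 2.035 (0.021) | 0.078 |

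This matches Table 3 to rounding. The table corresponds to gamma −4, whereas the text says −5; step 4 shows that this hardly matters here.

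**2. Standard error implied by Table 3.** The expected Z at full information is 3.588 when the ratio is 1.00. So SE of the log ratio at 130 patients = 0.1398/3.588 = 0.0390, and SE at look k = 0.0390 × √(6/k).

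**3. Hand check of early stops.**
- Non-safety stop at look 1: SE = 0.0390 × √6 = 0.0955. Z ≤ −0.663 means log ratio ≥ 0.1398 + 0.663 × 0.0955 = 0.2031. The lower 95% limit is then at least 0.2031 − 1.96 × 0.0955 = 0.016, above 0.
- Non-safety stop at look 2: SE = 0.0390 × √3 = 0.0675. Log ratio ≥ 0.1398 − 0.073 × 0.0675 = 0.1349. The lower limit is at least 0.1349 − 1.96 × 0.0675 = 0.003, above 0.
- So, at this SE, every non-safety stop at looks 1 or 2 yields an interval wholly above a ratio of 1, whatever the truth. These are 2 × 0.0167 = 3.3% of trials at a true ratio of 1.00.
- Safety stop at look 1: log ratio ≤ 0.1398 − 3.325 × 0.0955 = −0.178, so the reported ratio is at most 0.84.

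**4. Coverage by simulation** (about one million or more trials per setting; interval = estimate ± 1.96 SE at the stopping look; both boundaries acted on unless stated).

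| Setting | Coverage |
|---|---|
| True ratio 1.00 | 89.4% |
| True ratio 1.05 | 91.7% |
| True ratio 1.10 | 92.7% |
| True ratio 1.15 (the margin) | 95.1% |
| Ratio 1.00, gamma −5 as worded | 89.5% |
| Ratio 1.00, only the safety boundary acted on | 93.3% |

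At a ratio of 1.00 the misses make HES look too bad in 6.4% of trials and too good in 4.2% to 4.3%, depending on the run. The mean estimated ratio is 0.988 overall, 0.972 when noninferiority is declared and 1.136 otherwise. About 64% of non-safety stops exclude 1.

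**5. Dependence on the SE.** Coverage at a given ratio depends on (log 1.15 − log ratio)/SE. With a simple two-group SE = SD × √(4/130) and a ratio of 1.00:

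| Log-scale SD | Source | Coverage |
|---|---|---|
| 0.246 | CV 25%: √log(1.0625) | about 89.8% |
| 0.5 | assumed | 92.4% |
| 1.0 | assumed | 92.8% |
| about 1.35 | quartiles 13.5 and 82.9 in the sample size section: log(82.9/13.5)/1.349 | 93.4% |

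Baseline adjustment would shrink the SE by an amount that the documents do not give.

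**6. Remedies at a ratio of 1.00, both boundaries acted on.** Stage-wise ordering covers 95.0%. A repeated confidence interval using the safety boundary's Z at the stopping look covers 99.5%. Widening every interval to the final-look value of 2.035 reaches only 91.1%.

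**The case against.** **The noninferiority conclusion is safe.** A reader might infer that the upper limit falls below 1.15 too often and produces false noninferiority claims. The documents do not support that. A false claim needs a true ratio of at least 1.15. At exactly 1.15 the ordinary upper limit is too low in 2.2% of trials, under the nominal 2.5%, and the type I error of the Table 3 test is about 0.02. At a true ratio of 1.00, coverage among trials that declare noninferiority is 95.3%. This objection stands in full; the point concerns estimation only.

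**The error does not mainly flatter HES.** At a ratio of 1.00 more misses count against HES than for it, and the average bias over all trials is about 1%. That stands. Both directions nevertheless exceed 2.5%.

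**The 89% figure is near the worst case.** It needs Table 3's power to be realised and both boundaries to be acted on. The SE may be larger. Under EXECUTIVE COMMITTEE, that committee only recommends, and may weigh whether a trend could reverse. Recruitment may also continue during an interim analysis, and the simulation ignores such extra patients. These points stand, and they turn 89% into a range of about 89% to 93%. They do not restore 95%.

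**The plan never says the intervals are unadjusted.** True: both the ordinary method and the 95% level are inferred. But the mixed-model estimate and SE are the only ones specified, and silence leaves the choice open until the results are known.

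**Conclusion.** The gap is real and of moderate size. The plan emphasizes an estimate and interval for NGAL, lets the trial stop at any of six looks, and specifies no allowance for stopping in either quantity. For a truly equivalent fluid an ordinary 95% interval covers about 89% if Table 3 is realised and followed, and up to about 93% under a larger SE or if the non-safety boundary is disregarded. The most visible consequence is an apparent kidney harm after a non-safety stop. The share of such stops excluding 1 (about 64%) applies at Table 3's SE and falls as the SE grows.

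The result rests on an inferred 95% level, an inferred unadjusted method, equally spaced looks and no extra patients after a crossing. It is no ground for doubting the noninferiority test, and no evidence that the reporting favours HES.

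**What to change.** In the reporting paragraph and in Interim monitoring analyses, state that the headline urinary NGAL result, at whichever look the trial ends, is the median-unbiased ratio of geometric means with a 95% interval from stage-wise ordering. A repeated confidence interval using the stopping look's critical value is an acceptable, conservative alternative. Show the unadjusted mixed-model estimate and interval as a secondary figure, labelled as not allowing for the interim looks. The same text should give the confidence level and say how patients recruited while an interim analysis is running enter the final estimate.

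The cost is SAP wording and a few lines of standard group-sequential code. The interval will usually be somewhat wider. No extra patients are needed, and neither the boundaries nor the conduct of the trial changes.

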Continuous outcomes measured over time (Primary and secondary aims). For the primary outcome (urinary NGAL) and each of the secondary continuous outcomes which are measured over time (e.g., at baseline, within one hour of arrival to ICU following surgery, and 24 hours following completion of surgery), we will assess the treatment effect of HES 130/0.4 versus standard care using linear mixed effects models (with patient as random effect), adjusting for the baseline value of the outcome and any baseline variables for which balance among the randomized groups was not achieved through randomization. We will adjust for the baseline value of the outcome for efficiency, i.e., to obtain a smaller standard error for the estimate of treatment effect to the extent that the baseline value is correlated with the later time points, regardless of baseline balance. An unstructured within-subject correlation structure will be employed, estimating a distinct correlation parameter for each pair of post-baseline measurement times.

If the treatment group-by-time interaction is significant ($P < 0.15$), the treatment effect for a particular outcome will be assessed at each of the post-baseline time points measured, using a Bonferroni (or other appropriate) correction for multiple comparisons procedure if comparing groups at specific time points. Similarly, correction to the significance criterion will be made in all analyses below when comparing multiple times, as appropriate.

Ordinal outcome. Groups will be compared on the ordinal outcome of the RIFLE criteria (Secondary Aim 1) using proportional odds logistic regression, adjusting for baseline imbalance

as needed. We will assess noninferiority using the approach described above for the primary outcome, where $\hat{\beta}_1$ is the estimated treatment effect in the form of a log-odds ratio.

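### The main imputation rule ignores a patient's observed 24-hour NGAL when the ICU-arrival value is missing; the possible bias is small, leans toward noninferiority, and costs nothing to remove

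*Combined protocol and SAP*

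**What the plan says.** The missing-data paragraph under Statistical Methods applies to any missing primary or secondary outcome. Its main method is "multiple imputation of outcome values based on all available data before the time point of interest". It adds two further analyses:

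- a secondary analysis that gives missing HES values the worst observed value at that time and missing control values the best;
- if the amount missing is non-trivial (no threshold is given), a plan to "conduct sensitivity analyses on various forms of imputation (from none at all to full multiple imputation").

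The primary outcome is NGAL "measured within one hour of arrival to ICU and 24 following completion of surgery". The paragraph on continuous outcomes measured over time specifies "linear mixed effects models (with patient as random effect), adjusting for the baseline value of the outcome". It continues: "An unstructured within-subject correlation structure will be employed", "estimating a distinct correlation parameter for each pair of post-baseline measurement times". The Type I error paragraph says the model will "simultaneously assess the effect across the collapsed time points if there is no group-time interaction". On level and direction it says: "The significance level will be 0.025 for the 1-tailed noninferiority tests for the primary outcome".

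**The concern.** The two parts of the plan do not fit together. A mixed model with unstructured correlation, fitted to the observed data, uses the 24-hour value to inform a missing ICU-arrival value and is valid if data are missing at random given what was observed. Imputing first from baseline and arm alone removes that link: for the imputed patients, the ICU-arrival value becomes unrelated to the 24-hour value, given baseline and arm.

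This matters most if patients with unusual 24-hour values are also those who lack the first sample. Their imputed values are then drawn toward the average of the patients with samples, and a real difference between arms shrinks. In a noninferiority trial of safety, shrinking a harmful difference favours the claim that HES is acceptable. The affected sample is one of only two post-baseline values in the primary comparison, and the plan's time-point definitions place it where NGAL is expected to peak. The rule applies equally to other outcomes measured at ICU arrival.

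**Working it through.** The plan gives no figure that depends on this rule, so there is none to reproduce. The check asks what the rule does to the collapsed treatment effect.

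**Inputs from the documents.**
- Margin: ratio of geometric means 1.15; ln 1.15 = 0.1398.
- Coefficient of variation 25%; log-scale SD = √ln(1 + 0.25²) = 0.2462.
- Maximum 130 analysed, 65 per group; one-sided 0.025.
- Allowance of 5 dropouts: 5/(130 + 5) = 3.7%, taken as about 4%. No rate is given for missing ICU-arrival samples.

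**Assumptions not in the documents.** ICU/24-hour correlation 0.4 or 0.7; correlation of each with baseline 0.3; ICU-arrival value missing in 4%, 10% or 20%; missingness either completely random or dependent on the 24-hour value; arm included in the imputation model. Each scenario had 600 simulated trials and 10 imputations.

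**Step 1: correlation.** After adjustment for baseline, the correlation between the two times is (ρ − 0.3²)/(1 − 0.3²), which is 0.34 for ρ = 0.4 and 0.67 for ρ = 0.7. If a fraction m of ICU values is imputed without the 24-hour value, the estimate should fall to about (1 − m) times its value. With completely random missingness:
- 4% missing, ρ = 0.4: 0.330 × 0.96 = 0.317; simulated 0.316.
- 20% missing, ρ = 0.4: 0.327 × 0.80 = 0.262; simulated 0.257.
- 20% missing, ρ = 0.7: 0.662 × 0.80 = 0.530; simulated 0.522.

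**Step 2: precision, completely random missingness, true ratio 1.** Empirical standard error, plan's rule against mixed model on observed data:
- 4%, ρ = 0.4: 0.0354 against 0.0352 (ratio 1.006).
- 10%, ρ = 0.7: 0.0382 against 0.0379 (1.008).
- 20%, ρ = 0.4: 0.0358 against 0.0350 (1.023).

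Imputing with the 24-hour value gives the same standard error as the plan's rule to within 0.0003, so even this small loss is not clearly due to the restriction. The treatment effect is unbiased in this setting.

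**Step 3: bias, missingness dependent on the 24-hour value, true log ratio at the margin (0.1398).**

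| Missing | ρ | Plan's rule | Observed-data model | Shift | Imputed with 24-hour value | False noninferiority, plan / observed-data |
|---|---|---|---|---|---|---|
| 4% | 0.4 | 0.1396 | 0.1409 | 0.0013 | 0.1409 | 4.0% / 3.3% |
| 4% | 0.7 | 0.1381 | 0.1404 | 0.0023 | 0.1403 | 3.0% / 2.3% |
| 10% | 0.4 | 0.1360 | 0.1382 | 0.0022 | 0.1382 | 4.0% / 3.7% |
| 10% | 0.7 | 0.1338 | 0.1394 | 0.0056 | 0.1392 | 4.3% / 4.2% |
| 20% | 0.4 | 0.1367 | 0.1406 | 0.0039 | 0.1405 | 4.2% / 3.8% |
| 20% | 0.7 | 0.1310 | 0.1397 | 0.0087 | 0.1393 | 6.0% / 2.8% |

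As shares of the margin, the extremes are 0.0013/0.1398 = 0.9% and 0.0087/0.1398 = 6.2%. On the ratio scale the largest shift is from exp(0.1397) = 1.150 to exp(0.1310) = 1.140. A second simulation on the same kind of assumptions gave 0.137 to 0.138 at 4% and 0.133 to 0.136 at 20%, against a true 0.140.

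The error rates carry a Monte Carlo standard error of about 0.7 to 1 point and should be compared only within a row. Only the last row shows a clear difference.

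**The case against.** The strongest reply is that the plan already contains the remedy. Analysis with no imputation is the mixed model on observed values, and full multiple imputation plausibly uses all times. The worst/best-value analysis does not depend on how much is missing and is aimed at exactly the direction of bias feared here. Where missingness is too small to trigger the sensitivity analyses, the bias is negligible too. This stands as to size. It does not settle which analysis is primary: the trigger has no threshold, and an extreme bound does not correct the main estimate.

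Several stronger readings are tempting but not supported:

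- **The 24-hour NGAL is thrown away.** It is not. It is lost only as a predictor in the imputation and remains an outcome in the model. If only the 24-hour value is missing, the rule still uses baseline and ICU-arrival NGAL.
- **The mixed model loses real power.** Step 2 shows otherwise.
- **Samples will be missing because injured patients make little urine.** No section says so. Oliguric or anuric renal failure not related to hypovolemia and creatinine above 1.6 mg/dL are exclusions, and the time-point definitions provide for sampling when ICU transfer is delayed. The 5 dropouts allowed for may have no 24-hour value to use.
- **The primary ratio could be badly misread.** Suppose 15% against 5% of patients have tripled NGAL, half of those lack the first sample, and the log SD is 0.5. The first-sample ratio then falls from about 1.12 to 1.07. But these inputs are all assumed, the SD is about twice the plan's 0.246, and 1.12 already lies inside the margin. The primary effect collapses both times: with equal weights it moves from 1.116 to √(1.064 × 1.116) = 1.090, about half the shift.

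**Conclusion.** The point holds as a minor one. The main rule withholds information that the plan's own model would use, and no reason is given for doing so. The cost is a lowered ICU/24-hour correlation and, only if missingness is related to the 24-hour value, a bias that favours noninferiority when HES is truly worse. That bias is about 0.001 to 0.003 on the log scale near 4% missing and 0.004 to 0.009 at 20% missing, for correlations of 0.4 to 0.7 that the documents do not state. With no true difference and the same missingness process in both arms, symmetry implies no bias.

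A reader might infer that the primary conclusion is unsafe. At the planned level of loss it is not. A materially raised false-claim rate (6.0% against 2.8%) appeared only with 20% missing, correlation 0.7 and missingness tied to the 24-hour value together.

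**What to change.** Delete the restriction to data before the time point. Then name one primary approach:

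- the mixed model fitted directly to all observed values; or
- joint multiple imputation of the two post-baseline times from baseline, both post-baseline values and arm, followed by the same model.

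The first is simpler, particularly for the early interim looks at about 22 and 43 patients. Keep the worst/best-value analysis as secondary. Either approach removes the bias when missingness depends on observed values. Neither fully protects if it depends on unobserved injury: in the assumed injury scenario above, imputing with the 24-hour value gave a first-sample ratio of 1.105 against a true 1.119. That is why the worst/best-value analysis should stay.

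The cost is one phrase and one clarifying sentence, with no extra data or patients. Make the change before any unblinded analysis.
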